### **3. STUDY OBJECTIVES**

The primary objective of this study is to assess the efficacy of Merlin solution on the clinician assessed duration of the classical herpetic lesion as compared to placebo treatment. The duration of a classical lesion is defined as the time, in hours, from the beginning of treatment to the onset of Stage 6, or, if Stage 6 is never observed, Stage 7. A classical lesion is defined as one that progresses through any of the vesicle/pustule, ulcer, or crust stages (stages 3, 4 or 5).

The secondary objectives of this study are to compare the active and placebo treatment arms with regard to:

1. The clinician assessed duration of the herpetic episode. For a classical lesion, the duration of the herpetic episode is defined as the time, in hours, from the beginning of treatment until the loss of hard crust (stage 6; residual erythema can be present after loss of hard crust). For non-classical (aborted) lesions, duration is defined as the time, in hours, from the beginning of treatment until complete resolution of all local signs and symptoms (stage 7).
2. The clinician assessed duration until complete healing of the herpetic episode (classical and non-classical lesions) as compared to placebo treatment. For

both classical and non-classical lesions, the duration until complete healing of the herpetic episode is defined as the time, in hours, from the time of treatment until complete resolution of all local signs and symptoms (Stage 7).

3. The clinician assessed prevention of progression to a classical lesion associated with herpes labialis.
4. The clinician assessed lesion size (maximum lesion area; cumulative lesion area).
5. The clinician assessed duration of the herpetic lesion hard scab (end of stage 5/beginning of stage 6).
6. The safety of Merlin

Based on patient diary entries, other objectives of this study are to compare the active and placebo treatment arms with regard to:

7. Subject assessed duration and severity of lesion pain
8. Subject assessed duration of the classical herpetic lesion
9. Subject assessed duration of the herpetic episode
10. Subject assessed duration of complete healing of the herpetic episode
11. Subject assessed prevention of progression to a classical lesion
12. Subject assessed duration of the herpetic lesion hard scab
13. Subject assessed duration and severity of lesion pain.

More detailed explanations of these endpoints are provided in Section 10.7.

#### **4. SUMMARY OF STUDY DESIGN**

This current clinical study is a Phase 2 trial using the same Merlin formulation as was used in the Phase 1 TR-H-111 and Phase 2 TR-H-211 trials. The TR-H-111 study showed that Merlin appears to be safe to use even with repeated dosing over several days in healthy normal subjects. The Phase 2 TR-H-211 trial similarly demonstrated that Merlin was generally safe and tolerable in the treatment of subjects with lesions associated with herpes simplex labialis. TR-H-211 also revealed, in an a priori analysis, that those subjects who treated with Merlin at the first visible signs of a herpetic lesion, erythema, rather than immediately at first symptoms of a herpetic lesion, the prodromal stage, exhibited statistically significant efficacy as compared to placebo for the duration

of the classical lesion. The same a priori analysis found trends towards significance for the endpoints of complete healing, duration of the herpetic episode, cumulative lesion size, duration of the hard scab, and the subject assessed severity of lesion pain.

The present trial is designed to examine the efficacy and safety of treatment with Merlin as compared to treatment with placebo (10% ethanol) in subjects treating at first visible signs of a herpes labialis lesion (i.e. erythema [Stage 1] or papule/edema [Stage 2]).

Approximately four hundred and fifty (450) subjects, 18 to 75 years of age, who meet the eligibility criteria, including a history of at least 3 recurrences of herpes labialis in the preceding 12 months, will be enrolled into the study. Eligible subjects will be randomized in a 1:1 ratio to one of two treatment groups: 1) a treatment of three (3) applications of Merlin solution, performed within a time period of 40 minutes or less, while allowing time for the solution to dry on the lesion between applications; or 2) a treatment of three (3) applications of 10% ethanol, as a placebo, performed within a time period of 40 minutes or less, while allowing time for the solution to dry on the lesion between applications. A total of twelve (12) Merlin or placebo treatments, i.e. thirty-six (36) applications, will be administered over the ensuing ninety-six (96) hours (four (4) days) after the first treatment. On each day, treatments will be administered six (6) hours apart, with a maximum of three treatments each day. The first treatment will be administered on Treatment Day (Day 0), and then repeated at 6 and 12 hours after the first treatment, time permitting.

After being enrolled and randomized into the study, subjects will be sent home with a sealed kit containing a bottle filled with either Merlin (active) or 10% ethanol (placebo) and a packet of foam-tipped applicators sufficient to apply three study treatments (nine (9) applications). At first signs and/or symptoms of a recurrent herpetic episode (Stage 0, prodrome Stage 1, erythema, or Stage 2, papule/edema), subjects will call the clinic to confirm by telephone interview, the presence of a lesion and the lesion stage. Subjects reporting either a Stage 1 or Stage 2 lesion will be interviewed to review the eligibility criteria. If they meet all the eligibility criteria they will then be instructed to begin treatment immediately, thereby initiating the Treatment Phase of the study. Though subjects reporting a Stage 2, papule/edema, lesion will be allowed to treat, subjects should be strongly encouraged to call at the first visible signs of a herpetic lesion. A subject observing a lesion at Stage 1, erythema, therefore, should call in immediately rather than assume they may wait until their lesion reaches Stage 2, papule/edema, to call in. Subjects reporting only Stage 0 symptoms, i.e. no visible signs of a cold sore lesion, will be instructed to monitor their lesion and to call the clinic immediately upon observing any early visible sign of a cold sore, i.e. a Stage 1 or Stage 2 lesion. Once the subject calls in and confirms by telephone interview that their lesion has reached Stage 1 or 2, and that they still meet all eligibility criteria, they will be instructed to begin treatment immediately. Subjects will then be instructed to return to the clinic as soon as possible within 24 hours of starting treatment.

Subjects will report daily for a minimum of 3 consecutive days, with the last clinic visit at the time of complete healing (Stage 7 - normal skin) or at 14 days, whichever is earlier. Subjects will be contacted by phone, for a safety assessment, 2 weeks after they complete

the Treatment Phase of the study. Subjects will also be provided a diary that he or she will be instructed to fill out daily from the first day of treatment until the lesion is healed.

Both treatment groups will continue to accept subjects into the Treatment Phase of the study until there are at least seventy five (75) subjects in each group. Once the enrollment objectives for the Treatment Phase of the study have been met, the study will be closed to any further enrollment.

**Table 4-1: Treatment Groups and Sample Sizes**

Group	Treatment	Approximate Number of Randomized Subjects	Minimum Number of Subjects Entering Treatment Phase
A	Merlin (10% ethanol; 0.6% glycolic acid)	225	75
B	Placebo (10% ethanol)	225	75

Aside from any placebo effect, there should be no efficacy with the 10% ethanol solution.

## 5. SUBJECT SELECTION

### 5.1 Source of Subjects

Non-institutionalized subjects consisting of members of the community at large will be used in this study.

Approximately four hundred and fifty (450) subjects with a history of recurrent herpes labialis, who meet the eligibility requirements, will be randomly assigned to one of two treatment groups and provided with study materials. Upon noticing visible signs of a herpes labialis lesion which meet the study criteria, the subject will call their clinical study site at which time he or she will be required to answer specific questions to confirm if he or she meets the eligibility requirements. If the subject is eligible for entry into the Treatment Phase of the study, the subject will be instructed to begin treatment immediately. The study will continue until at least 75 subjects have entered the Treatment Phase in each group (Table 4-1), at which time the study will be closed to any further enrollment.

### 5.2 Study Enrollment Eligibility Criteria

The following criteria will be used for the initial Screening-Randomization visit. The Vice President of Clinical Research at Topical Remedy, their designee, or the Medical Monitor, should be consulted to confirm the eligibility of a subject if there is any question as to whether they meet all of the Inclusion or Exclusion criteria.

### **5.2.1 Inclusion Criteria**

1. Male or female subject 18-75 years of age
2. Female subjects must be using a medically acceptable form of birth control during the study. Acceptable birth control measures include, but are not limited to: abstinence, oral contraceptive pills or patch, injectable contraception, barrier contraceptives (condom, diaphragm with spermicide), IUD, vaginal contraceptive ring, surgical (hysterectomy, tubal ligation), vasectomized partner, and natural post-menopausal inability to conceive. Menopause is defined for this protocol as starting one year after the time of the last menstrual period.
3. Subject must have a history of recurrent herpes labialis and report at least 3 separate recurrences (i.e. multiple herpetic lesions in one outbreak count as only one episode) during the preceding 12 months.
4. Subject must have a history of experiencing prodromal symptoms of cold sores (e.g. itching, tingling, or burning) during at least half of their previous cold sore episodes.
5. Subject must have a history of at least half of their cold sore episodes producing classical lesions (i.e., episodes that progressed through macule, papule, vesicle, crust, and healed).
6. Subject must provide voluntary written informed consent to participate in this study.

### 5.2.2 Exclusion Criteria

1. Subjects with evidence of active malignancy or immunodeficiency disease within the last 30 days. Subjects who have completed therapy and are considered unlikely to relapse or who have had surgery and do not have any evidence of disease, are eligible for the study.
2. Subject requires chronic use of immunomodifying drugs (e.g. systemic steroids) or topical steroids on or near the face; use of inhaled steroids does not exclude a subject from the study. If a subject is unlikely to get through the Treatment Phase of the protocol without requiring the use of an immunomodifying drug for a chronic condition the subject should be excluded.
3. Subject requires chronic use of anti-viral medication.
4. In females of childbearing potential, a positive urine pregnancy test at time of screening.
5. Nursing mothers.
6. Subject is considered unreliable or unable to understand or follow the protocol directions or is unable to comprehend or satisfactorily assess a herpetic lesion as determined by Investigator or designee at screening.
7. Subject has abnormal skin conditions (e.g. acne, eczema, rosacea, psoriasis, albinism, or chronic vesiculobullous disorders) that occur in the area ordinarily affected by cold sores or has significant facial hair in the area of the cold sore that might affect the normal course of the cold sore or might impair accurate evaluation of the cold sore lesion.
8. Subject has had a vaccine for herpes simplex virus type 1 (typically oral herpes) or 2 (typically genital herpes).
9. Subject is currently enrolled in another clinical trial involving the use of a drug and/or a device.
10. Subject has previously participated in the current study (TR-H-212).
11. Subject requires chronic use of analgesics or non-steroidal anti-inflammatory agents (NSAIDs) except for low doses of aspirin ( $\leq 325$  mg/day) used for cardiovascular purposes. If a subject is unlikely to get through the Treatment Phase of the protocol without requiring the use of analgesia for a chronic condition, e.g. back pain, recurrent daily headaches, the subject should be excluded.
12. Subject has a recent history of renal dysfunction or serious hepatic disease.

Renal dysfunction encompasses both acute and chronic renal failure, the former resulting from the sudden loss of the ability of the kidneys to excrete wastes, concentrate urine, and conserve electrolytes and the latter the gradual and progressive loss of these capabilities.

Examples of serious hepatic disease would include alcoholic liver disease, chronic hepatitis, autoimmune hepatitis and a variety of inherited diseases. The underlying cause of a documented recent mild increase in liver enzymes should be considered when deciding whether or not to exclude such a subject.

13. Subject has a history of alcoholism or drug abuse within the preceding 12 months. A subject with a history of a pathological pattern of alcohol use that causes a serious impairment of social or occupational functioning should be excluded. Such subjects may exhibit symptoms of tolerance and withdrawal along with other behavioral symptoms.
14. Subject shares a household with another subject already enrolled in the study (TR-H-212). If the other household member has already completed the study, then the currently enrolling subject is not excluded.
15. Subject is institutionalized.
16. Any history which, in the Investigator's judgment, makes the subject ineligible or places the subject at undue risk.

### 5.3 Study Treatment Phase Eligibility Criteria

The following criteria will be used to enter subjects into the study Treatment Phase when a subject previously enrolled into the study calls to report first visible signs of a herpes simplex labialis lesion. Subjects who call in to report experiencing prodromal symptoms (e.g. tingling, itching) are not to be screened for eligibility until they report observing visible signs of a cold sore lesion. The Vice President of Clinical Research at Topical Remedy, their designee, or the Medical Monitor, should be consulted to confirm the eligibility of a subject if there is any question as to whether they meet all of the Inclusion or Exclusion criteria.

#### 5.3.1 Inclusion Criteria

1. Subject has a visible herpes simplex labialis lesion, in an area around the mouth, assessed by the subject, and confirmed by telephone contact, to be at the erythema stage (Stage 1) or Papule/Edema stage (Stage 2) as defined below:

**Stage 1:** **Erythema stage** is defined as any redness with no skin swelling or other signs of advanced stages.

**Stage 2: Papule/Edema stage** is defined as any skin swelling or solid raised area above the normal surface without evidence of more advanced stages such as fluid filled blisters.

2. Female subjects must be using a medically acceptable form of birth control during the study. Acceptable birth control measures include but are not limited to: abstinence, oral contraceptive pills or patch, injectable contraception, barrier contraceptives (condom, diaphragm with spermicide), IUD, vaginal contraceptive ring, surgical (hysterectomy, tubal ligation), vasectomized partner, and natural post-menopausal inability to conceive. Menopause is defined for this protocol as starting one year after the time of the last menstrual period.
3. Subject has immediate access to the kit containing the clinical trial material. (The subject will demonstrate access to the clinical trial material kit by reading the Randomization Number printed on the label on the kit.)
4. Subject is able to appear for a clinic visit within 24 hours from the time of enrollment into the Treatment Phase of the study (from the time the subject called to establish entry into the Treatment Phase of the study) and is able to return to the clinic for the full 14 day duration of the study if necessary.

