## **10.4 General Methodology**

All statistical tests will be done using two-sided tests and a Type I error rate of 0.05.

Data listings will be based on all subjects in the safety population.

Continuous variables will be summarized using descriptive statistics, specifically the mean, median, standard deviation, minimum and maximum values. Categorical variables will be summarized by frequencies and percentages.

The primary analyses will compare the active treatment arm to the placebo control arm. Aside from any placebo effect, there should be no efficacy associated with the placebo solution. As a secondary analysis, all statistical comparisons will be performed with the treated subjects stratified based on whether they treated at erythema (Stage 1) or papule/edema (Stage 2).

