#### **10.7.9 Sample Size Determination**

The sample size for this study was based upon the results of the previous Phase 2 study, TR-H-211. In that study, Merlin demonstrated a statistically significant ( $p=0.0276$ ) effect on the duration of classical lesion endpoint for subjects beginning treatment at Stage 1 (erythema) with only 32 subjects treated with Merlin and 22 placebo subjects. Clinical investigations with Famvir and other independent studies, that initiate treatment within hours of the onset of prodromal symptoms (Stage 0) have demonstrated that 1/3 of all subjects enrolled in herpes labialis studies will have spontaneously aborted lesion. Any calculation of clinical trial size, therefore, must consider that factor. When, however, treatment is initiated at the erythema stage (Stage 1), as in the Merlin Phase 2a (TR-H-211) study, the incidence of spontaneously aborted lesions declines to 25%. As a result, a larger percentage of subjects will demonstrate classical lesions in Merlin studies than was seen in the Famvir, or similar previous studies. This was factored in when performing

power calculations for this Phase 2b clinical study. Those calculations determined that 144 subjects would provide a 95% likelihood of statistical significance for the herpetic episode endpoint. Merlin decreased the duration of herpetic episode in subjects that began treatment at stage 1 by 41 hours, with a p-value of 0.055 in the Phase 2a study. The herpetic episode endpoint includes the subjects with aborted lesions.

As a result, a 150 subject clinical trial will have approximately 60 subjects progress to classical lesions in each treatment arm and we can be highly confident of having the power to demonstrate a highly significant difference for the duration of classical lesion endpoint, as shown in the Phase 2a results. In addition, a 150 subject clinical trial should have greater than 95% likelihood of demonstrating a statistically significant Merlin effect on herpetic episode as a secondary endpoint.

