### 3 Sample Size

The sample size for this study was based upon the results of the previous Phase 2 study, TR-H-211. In that study, Merlin demonstrated a statistically significant ( $p=0.0276$ ) effect on the duration of classical lesion endpoint for subjects beginning treatment at Stage 1 (erythema) with only 32 subjects treated with Merlin and 22 placebo subjects. Clinical investigations with Famvir and other independent studies, that initiate treatment within hours of the onset of prodromal symptoms (Stage 0) have demonstrated that 1/3 of all subjects enrolled in herpes labialis studies will have spontaneously aborted lesion. Any calculation of clinical trial size, therefore, must consider that factor. When, however, treatment is initiated at the erythema stage (Stage 1), as in the Merlin Phase 2a (TR-H-211) study, the incidence of spontaneously aborted lesions declines to 25%. As a result, a larger percentage of subjects will demonstrate classical lesions in Merlin studies than was seen in the Famvir, or similar previous studies. This was factored in when performing power calculations for this Phase 2b clinical study. Those calculations determined that 144 subjects would provide a 95% likelihood of statistical significance for the herpetic episode endpoint. Merlin decreased the duration of herpetic episode in subjects that began treatment at stage 1 by 41 hours, with a p-value of 0.055 in the Phase 2a study. The herpetic episode endpoint includes the subjects with aborted lesions.

As a result, a 150 subject clinical trial will have approximately 60 subjects progress to classical lesions in each treatment group and we can be very confident of having the power to demonstrate a highly significant difference for the duration of classical lesion endpoint, as shown in the Phase 2a results. In addition, a 150 subject clinical trial should have greater than 95% likelihood of demonstrating a statistically significant Merlin effect on herpetic episode as a secondary endpoint.

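### The TR-H-211 results used for sizing come from Stage 1 starters, but the trial also admits Stage 2 starters without a limit, so the stated power is not shown to apply to the population enrolled

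*Protocol*

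**What the plan says.** **Entry.** Protocol 5.3.1 requires a visible lesion "confirmed by telephone contact, to be at the erythema stage (Stage 1) or Papule/Edema stage (Stage 2) as defined below". Protocol 4 and 7.2.1 urge subjects to call at Stage 1, but set no cap, target share or minimum number of Stage 1 starters. Accrual continues to at least 75 treated subjects per group, whatever their stage.

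**Planning basis.** Protocol 10.7.9, repeated in SAP 3, reports the TR-H-211 result on classical lesion duration (p = 0.0276) "for subjects beginning treatment at Stage 1 (erythema) with only 32 subjects treated with Merlin and 22 placebo subjects". The 25% aborted rate is introduced with "When, however, treatment is initiated at the erythema stage (Stage 1), as in the Merlin Phase 2a (TR-H-211) study". The only effect in hours is also a Stage 1 figure: "Merlin decreased the duration of herpetic episode in subjects that began treatment at stage 1 by 41 hours", with p = 0.055. Protocol 2 describes TR-H-211 callers as being at Stage 0 or 1.

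**Conclusion drawn.** The calculations are said to show that "144 subjects would provide a 95% likelihood of statistical significance for the herpetic episode endpoint". For the primary endpoint no power is given, only a statement of high confidence that rests on the TR-H-211 results and about 60 classical lesions per arm.

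**Analysis.** The main MITT test of duration is a Wilcoxon rank sum test with a Hodges-Lehmann estimate and no stage term (Protocol 10.7, SAP 7.13.1). On stage, Protocol 10.4 says: "As a secondary analysis, all statistical comparisons will be performed with the treated subjects stratified". SAP 7.2 and 7.13.5 likewise place the by-stage comparisons after or in addition to the pooled ones.

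**The concern.** The sponsor's own text treats starting stage as important. The introduction says that lesions mature within 8 hours and leave little time for intervention. Section 10.7.9 says that the aborted rate depends on starting stage (1/3 from prodrome, 25% from erythema). Sections 2 and 4 attribute the TR-H-211 signal to starting at erythema rather than prodrome. Even so, the power statements carry Stage 1 results to a population of unknown Stage 1 and Stage 2 mix and say nothing about the difference.

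Two things are at stake. First, if Stage 2 starters respond less, the pooled effect is diluted and the trial has less power than a reader of 10.7.9 would believe. Second, duration runs from first treatment, so Stage 2 starters may have a different expected duration. Randomisation takes place at enrolment and cannot balance stage at outbreak. An unstratified test then carries that variation as noise.

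**Working it through.** **Inputs from the documents.** "All statistical tests will be done using two-sided tests and a Type I error rate of 0.05"; 1:1 allocation; 32 and 22 Stage 1 subjects; p = 0.0276 (classical lesion) and p = 0.055 with 41 h (herpetic episode); 25% aborted; 75 treated per arm. **Assumed, because the documents do not give them:** Stage 2 share f and Stage 2 effect relative to Stage 1, e. The diluted effect is the Stage 1 effect times k = 1 − f + f·e.

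**The plan's own figure.** No SD is stated, so 144 subjects for 95% power cannot be fully reproduced. Back-solving from p = 0.055 (z = 1.919) gives SD = 41 / (1.919 × √(1/32 + 1/22)) = 77.1 h. With 72 per arm, two-sided power is then 89%. That shortfall is a separate question. To isolate the Stage 2 issue I use the SD at which the plan's figure is true: 41 / ((1.960 + 1.645) × √(2/72)) = 68.2 h.

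**Herpetic episode, 75 per arm.** Power = Φ(41k / (68.2 × √(2/75)) − 1.96), and 68.2 × √(2/75) = 11.14.
- Equal effect, k = 1: Φ(3.68 − 1.96) = 95.7%.
- Half effect, f = 20%, 40%, 60% (k = 0.9, 0.8, 0.7): Φ(1.35) = 91%, Φ(0.98) = 84%, Φ(0.62) = 73%.

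**Primary endpoint.** p = 0.0276 gives z = 2.203. Two readings of the 32 and 22 are possible:
- as classical-lesion counts: d = 2.203 × √(1/32 + 1/22) = 0.610;
- as all Stage 1 subjects, 75% of them classical (24 and 16.5): d = 2.203 × √(1/24 + 1/16.5) = 0.704.

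Classical lesions per arm: 75 × 0.75 = 56. The plan says about 60, which would mean 20% aborted. Power = Φ(d·k·√(56/2) − 1.96):

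| Stage 2 share and effect | d = 0.610 | d = 0.704 |
|---|---|---|
| Equal effect, any share | 90% | 96% |
| Half effect, 20% | 83% | 92% |
| Half effect, 40% | 73% | 85% |
| Half effect, 60% | 62% | 74% |

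With 60 per arm the equal-effect values are 91.6% and 97.1%. With no Stage 2 effect at all, a stress case, d = 0.610 and 56 per arm give 73%, 49% and 25%.

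**Stratified against pooled test.** Simulated power, 6,000 trials of 56 per arm, d = 0.61, equal effect, at Stage 2 shares of 30% and 50%:

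| Stage difference in duration | Stratified (van Elteren) | Pooled Wilcoxon |
|---|---|---|
| 0 | 87.5%, 87.0% | 87.8%, 87.5% |
| 0.1 SD | 87.5%, 87.4% | 87.9%, 88.0% |
| 0.3 SD | 87.3%, 86.0% | 87.5%, 86.2% |
| 0.5 SD | 87.0%, 87.3% | 86.2%, 85.8% |
| 1 SD | 87.7%, 87.5% | 81.4%, 79.9% |

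With no stage difference in duration and half the effect at Stage 2, the stratified test has 75.6% and 63.2% against 75.8% and 64.2% pooled. It does not recover diluted power. The simulated pooled values lie slightly below the 90% above because that figure is a normal-theory value for a comparison of means.

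**The case against.** The strongest reply has four parts.

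- *Stage is already handled.* Every comparison is prespecified by stage in both documents, so a weaker Stage 2 effect would be visible in planned output. This stands, and a reader who inferred that the plan ignores stage would be wrong. The by-stage results nevertheless change neither the primary p-value nor the basis of the stated power.
- *The scenarios are invented.* It is true that no Stage 2 share or effect appears in the documents. The plan also pushes towards Stage 1, by encouragement and by re-contacting prodrome callers every 6 to 18 hours. A reader might infer that the trial is underpowered or that the stated confidence is false. The documents do not support that. Power is unchanged if the Stage 2 effect is equal, and if aborted lesions are fewer with a later start, there would be more classical lesions to analyse.
- *Not every planning figure is a Stage 1 figure.* Correct: the 1/3 aborted rate comes from prodrome-initiated studies. It is quoted for contrast and then set aside in favour of 25%.
- *Stratifying gains little.* Largely correct. If the back-solved 77 h is a fair SD, a head start of 8 hours is about 0.1 SD and 0.3 SD is about 23 hours, and in that range the simulation shows no gain. Chance imbalance is minor too. At 75 per arm and a 50% share, the between-arm difference in Stage 2 share has an SD of √(2 × 0.5 × 0.5 / 75) = 8 points. Over a 24-hour stage difference that is about 2 hours, against a planning effect of 41 hours for herpetic episode.

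**Conclusion.** The concern holds as a gap in the support for the power statements. The TR-H-211 results used for sizing describe Stage 1 starters, the trial enrols Stage 1 and Stage 2 starters in unknown proportion, and nothing in either document links the two. The 95% for herpetic episode and the confidence expressed for the primary endpoint are not shown to apply. They carry over under an equal Stage 2 effect and are too favourable under a smaller one.

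The possible loss at half effect and shares of 20% to 60% runs from 4 points (96% to 92%) to 28 points (90% to 62%), depending on the share and on how the 32 and 22 are read. These figures rest on assumed shares and effects, on a standardised effect back-solved from a p-value, and on 56 classical lesions per arm held fixed.

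Dilution of the effect is the main issue and the lack of stratification a minor one. A reader might go further and infer that Stage 2 callers should not be admitted. That is a clinical decision on which the documents provide no statistical evidence, and no change to eligibility is proposed.

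**What to change.** 1. In Protocol 10.7.9 and SAP 3, state that the TR-H-211 planning results are for subjects who began treatment at Stage 1. Replace the unqualified statements for both endpoints with power over a stated range of Stage 2 share and relative effect. Say whether the 32 and 22 are classical lesions or all Stage 1 subjects, since the answer moves the projection by several points.

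2. As a cheap improvement, make the primary comparison a Wilcoxon test stratified by stage at first treatment (van Elteren), with a matching stratified Hodges-Lehmann estimate. Keep the planned by-stage results as supportive. SAP 7.13 can be read as making the efficacy analysis itself stratified, while Protocol 10.4 and SAP 7.13.5 put the pooled analysis first, so the primary test should be stated unambiguously in any case.

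Both are wording changes to be made before unblinding. Stage before first treatment is already collected at the telephone call and in the diary, so no new data or subjects are needed. The costs are a less favourable power statement and a loss of up to about 1 point if stage does not affect duration. The gain from stratifying is negligible up to about 0.3 SD, about 1 point at 0.5 SD and about 6 to 8 points at 1 SD. It does not restore power lost to a weaker Stage 2 effect, so the second change cannot replace the first.
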